## 7. HANDLING OF MISSING DATA

If there is no measurement within the acceptance range for the definition of visit timing for laboratory test values and efficacy endpoints (Appendix 11.1.1), data at the visit timing will be handled as missing.

If data on SDAI, CDAI, DAS28, TJC, SJC, patient VAS, physician VAS, ESR, or CRP is missing on Months 3 and 6, missing data will be imputed by LOCF using observed data after dosing for a sensitivity analysis on efficacy.

If the seriousness of, procedure for, and outcome of, adverse events are missing, they will be tabulated as "unknown."

If the date of event or death is missing for the analysis in consideration of time to the onset of malignant tumor and serious infection, and death, such a date will be imputed by the date on which no event or death is confirmed from among all data collected. The earliest of such date to complement the data would be the date on which the administration of Xeljanz or control drug therapy is started.

If the final date of dose or observation is missing, such a date will be complemented by the date on which a dose or observation is confirmed from among all data collected. The earliest of such date to complement the data would be the date on which the administration of Xeljanz or control drug therapy is started.

If candidate covariates (6.3) are missing (including unknown), they are not complemented in the univariate analysis. They are regarded as "unknown" and analyzed as one category in the multivariate analysis.

They are complemented by the multiple imputation method in the comparison of the Xeljanz group and the control group.

The death cases described in Section 6.1.1 define the cases in which treatment was not discontinued and continued until the end of the survey, or the cases in which no discontinuation was reported in the follow-up after discontinuation of treatment and death was reported within 3 years + 28 days from the start of treatment.

These are cases that meet the following two conditions and are regarded as cases in which the survey was discontinued due to death (the reason for discontinuation of the survey was death) in the comparison of deaths.

- Cases in which treatment has not been discontinued due to transfer or no return visit, and there is no reason for discontinuation of the survey.
- Cases in which death was reported as the reason for the seriousness of the serious adverse event and the outcome was within 3 years + 28 days from the start of the treatment, or an adverse event leading to death was reported and the death date was within 3 years + 28 days from the start of the treatment.

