## 1 Objective

The objective of this Surveillance is to verify the following subject matters concerning Xeljanz® Tablets (hereinafter referred to as “Xeljanz”) under post-marketing actual status of use.

- 1) Occurrence of adverse reactions, factors that may potentially affect safety, and effectiveness
- 2) Long-term safety (particularly, malignant tumors and serious infections) and effectiveness

Occurrences of malignant tumors and serious infections will be compared with a control group.

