#### [Rationale for sample size]

The incidence of malignant tumor associated with Xeljanz in a domestic long-term administration study (Study No. A3921041) was 1.16 (/100 person-year). The drop-out rate in clinical studies was 31% among subjects who transferred from the domestic Phase II study (Study No. A3921039) to the domestic long-term administration study (Study No. A3921041) (treatment period: approximately 3 years), and 14% among subjects who transferred from another domestic Phase II study (Study No. A3921040) (treatment period: approximately 1.4 years); based on which, the drop-out rate at the completion of 3-year observation in daily medical practice is estimated to be approximately 50%.

If 4000 patients were to be enrolled in the Xeljanz group, the target events should be confirmable in 104 patients based on the incidence of malignant tumor in Japanese subjects, which was 1.16 (/100 person-year).

Next, assuming that 4000 patients would be enrolled in the Xeljanz group and the incidence of malignant tumor in the control group would be equivalent to the Xeljanz group, at least 2000 subjects would need to be enrolled in the control group in order to enable a statistically appropriate inter-group comparison; thus, a sample size of 2000 subjects was selected for control.

Depending on the progress of registration, if the registered number of patients in either group significantly exceeds the above number earlier than the other group, a sample size with 3-year observation period can be changed to the combination of a sample size for whom the degree of statistical accuracy is maintainable if it is compared with 4000

patients in the Xeljanz group and 2000 patients in the control group (see the Appended Table). Also, the registration period for patients in the inter-group comparison needs to be the same.

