## 6.5 Observation period

### [1] Xeljanz group:

- (1) Registered subjects up to a certain sample size exceeding 3000 subjects from the start of registration: 3 years (36 months) from the date of treatment start
- (2) Registered subjects after the above (1): Only 6 months from the date of treatment start

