### [2] Control group: 3 years (36 months) from the date of treatment start

### [3] Type of survey form

Booklet-type survey form will be used for this Surveillance.

Safety and effectiveness will be evaluated on the day of the initial office visit after the end of the observation period for each booklet (including the day on which the observation period ends). However, the safety and effectiveness will be evaluated based on the information from the last known visit if the subject is lost to follow up during the treatment period.

The effectiveness evaluation will be performed on Xeljanz group only.

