### 1) Clinical laboratory tests

The results of clinical laboratory to the start of treatment (within 1 month prior to the start of treatment including the date treatment is commenced) and during and until the completion/discontinuation of the observation period should be recorded. If the observation period is discontinued, the test results at the time of discontinuation should be recorded if at all possible.

- [1] Hematological test: WBC, neutrophil, lymphocyte, RBC, platelets, and hemoglobin

\*Results of tests performed prior to the start of treatment (within 1 month prior to the start of treatment including the date treatment is commenced) and at 1, 3, 6, 12, 24, and 36 months of treatment will be essential.

- [2] Chemistry: AST (GOT), ALT (GPT), AL-P, LDH, HDL-C, LDL-C,  $\gamma$ -GTP, total bilirubin, triglyceride, serum creatinine and creatine kinase

\*Results of tests performed prior to the start of treatment (within 1 month prior to the start of treatment including the date treatment is commenced) and at 1, 3, 6, 12, 24, and 36 months of treatment will be essential.

- [3] Other tests: KL-6,  $\beta$ -D-glucan, and BUN

2) Chest X-ray or CT

Tests before treatment start and 12, 24, and 36 months after treatment start are considered essential.

3) Interferon  $\gamma$  (Quantiferon test, T-SPOT test, etc.)/tuberculin reaction

Tests before treatment start are considered essential.

4) Blood pressure (systolic/diastolic)

Tests before treatment start and 6, 12, 24, and 36 months after treatment start are considered essential.

5) Hepatitis B/C virus tests (HBs antigen, HBs antibody, HBc antibody, HBV-DNA, and HCV-antibody)

Tests before treatment start are considered essential. After treatment start, indicate whether HBV-DNA tests have been performed.

6) Assessment variables

The following assessment variables [1] to [6] will be evaluated.

The observation period will be as follows. If the observation period is discontinued, the test results at the time of discontinuation should be recorded if at all possible.

- Essential assessment timepoints: Assessment performed prior to the start of treatment (within 1 month prior to the start including the date treatment is commenced) and at 6, 12, 24, and 36 months of treatment (until completion of the observation period).

[Assessment variables]

[1] Tender joint count (evaluation of 28 joints)	[2] Swollen joint count (evaluation of 28 joints)

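### Effectiveness at Months 12, 24 and 36 is summarised only in patients still treated and assessed, and in the visible text no sensitivity analysis for missing values goes beyond Month 6

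*SAP*

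**What the plan says.** The second objective in Protocol 1 reads "Long-term safety (particularly, malignant tumors and serious infections) and effectiveness". Effectiveness is evaluated in the Xeljanz group only. Protocol 7.2 item 6) makes the joint counts, VAS scores, CRP and ESR essential before treatment and at Months 6, 12, 24 and 36.

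SAP 7 treats a visit with no measurement in its acceptance window as missing. For effectiveness variables missing at Months 3 and 6, "missing data will be imputed by LOCF using observed data after dosing for a sensitivity analysis on efficacy". SAP 8.2.4.1 and 8.2.4.2 repeat the Month 6 limit for SDAI, CDAI, DAS28, EULAR response and the components. The multiple imputation in SAP 7 and 8.1.6 is for covariates in the comparison of the two groups, not for effectiveness.

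Protocol 7.2 asks for test results only up to the end of observation or the date of discontinuation. Follow-up after discontinuation (Protocol 6.5 [4] and 7.7) collects drug use and selected adverse events, but no effectiveness. Protocol 7.3 lists both remission and inadequate clinical response among the reasons for stopping.

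Two further passages matter. Protocol 6.5 [3] says that "the safety and effectiveness will be evaluated based on the information from the last known visit if the subject is lost to follow up" during treatment. The sample-size rationale in Protocol 3 says that "the drop-out rate at the completion of 3-year observation in daily medical practice is estimated to be approximately 50" per cent.

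**The concern.** A patient who stops before Month 12, 24 or 36 normally has no value in that window and leaves both numerator and denominator. If patients doing poorly stop more often than patients doing well, remission can rise from visit to visit, and mean disease activity can fall, without any patient improving. The 95% confidence interval planned for the remission proportion reflects sampling error among those assessed and says nothing about those who left.

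At stake is how the late figures are read. A Month 36 remission rate reported without qualification is easily taken as the share of patients starting the drug who are in remission three years later. The planned analysis does not estimate that.

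**Working it through.** **Inputs from the documents.** Planned Xeljanz group 4000; malignancy rate 1.16 per 100 person-years; assumed 3-year drop-out about 50%; domestic study drop-out 31% over about 3 years (all Protocol 3). The cohort scheduled for 3 years is 3000 to 4000, so 0 to 1000 patients are scheduled for 6 months (Protocol Appendix).

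**Assumption.** The documents give no remission rate. Observed-case remission at Month 36 is varied from 20% to 50%.

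**Step 1: how the plan uses its 50%.** With linear loss to 50% at 3 years, person-years = 4000 × 3 × (1 − 0.5/2) = 9000. Events = 9000 × 0.0116 = 104.4, which matches the stated 104. Other loss patterns do not match: exponential loss gives 100.4, no loss 139.2, and half lost at the outset 69.6. So 50% is the plan's working figure, although it was set for malignancy.

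**Step 2: retention by visit.** Linear: 1 − 0.5 × m/36. Exponential: exp(−ln 2 × m/36).

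| Month | Linear | Exponential |
|---|---|---|
| 12 | 83% | 79% |
| 24 | 67% | 63% |
| 36 | 50% | 50% |

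At Month 36 this leaves 3000 × 0.5 = 1500 to 4000 × 0.5 = 2000 patients, if everyone retained is assessed.

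**Step 3: leavers counted as not in remission.** Rate over the 3-year cohort = observed rate × retained share. At Month 36:

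| Observed (assumed) | 31% drop-out (× 0.69) | 50% drop-out (× 0.50) |
|---|---|---|
| 20% | 13.8% | 10% |
| 30% | 20.7% | 15% |
| 40% | 27.6% | 20% |
| 50% | 34.5% | 25% |

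The gap is smaller earlier. With linear loss to 50%, an observed 30% becomes 25% at Month 12 and 20% at Month 24.

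**Step 4: comparison with the planned interval.** At an observed 30% with 50% drop-out, the extremes are 0.30 × 0.50 = 15% (no leaver in remission) and 0.15 + 0.50 = 65% (every leaver in remission). With 31% drop-out they are 20.7% and 0.207 + 0.31 = 51.7%. The half-width of the planned 95% interval is 1.96 × √(0.3 × 0.7/n), which is 2.3 points for n = 1500 and 2.0 points for n = 2000.

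**The case against.** - **Attrition will be visible.** SAP 8.1.1 makes the number of patients a standard summary statistic. SAP 8.2.1 and Table 2 tabulate discontinuation by reason and time in the efficacy set, with remission and inadequate effect as separate reasons. This stands, and those tables need not be requested again. They do not express remission over the cohort that started.
- **Stakes are limited.** Effectiveness is single-group, SAP 4 calls all tests exploratory, and the visible effectiveness tests (SAP 8.2.4.3) use Month 6 remission. This also stands. The issue is interpretation of late rates, not error control.
- **The size is illustrative.** The remission rates are assumed. The 50% was set for malignancy, whose follow-up continues after the drug is stopped, so it is not clearly drug retention. This is why the 31% figure is shown beside it.
- **Direction.** A reader might infer that late remission is bound to be overstated. The documents do not support that: leavers include patients who stopped in remission, transferred or did not return, and the mix is not given. Overstatement is plausible but not shown.
- **Conflict with the protocol.** A reader might infer that Protocol 6.5 [3] requires the last value to be carried to Month 36 and that the SAP disobeys it. The rule covers only patients lost to follow-up, which is narrower than all who discontinue, and states no carry-forward to later visits. What remains is that its relation to the SAP 7 visit windows is unclear.

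**Conclusion.** The point holds in a limited form. In the visible text, effectiveness at Months 12, 24 and 36 is an observed-case summary with no sensitivity analysis for missing values. The rates describe patients still treated and assessed in the window, and may overstate long-term effectiveness.

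Under the assumed observed rates of 30% and 40%, counting leavers as not in remission lowers the Month 36 figure by 9.3 and 12.4 points with 31% drop-out (30 − 20.7; 40 − 27.6), and by 15 and 20 points with 50%. These figures assume that everyone retained is assessed and that no leaver is in remission.

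Two stronger readings go too far. A reader might infer that the late rates include only patients who stayed on the drug. Protocol 7.2 asks for values at discontinuation where possible, and such a value can fall in a late window (Month 36 opens at Day 1052 in SAP Appendix 11.1.1). Conversely, patients still on treatment without a measurement in the window are also left out. A reader might also infer that no late sensitivity analysis exists at all. Text is redacted after the effectiveness sentence in Protocol 8.3 and after SAP 8.2.4.3, so the statement is confined to what can be read.

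**What to change.** In SAP 8.2.4, at Months 12, 24 and 36:

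1. Beside the observed-case result, add remission and response with patients who discontinued before the visit counted as not in remission or response.
2. Use only the cohort scheduled for 3-year observation as denominator. The efficacy set also contains patients whose observation is "Only 6 months from the date of treatment start" (Protocol 6.5 [1]); they have no later value by design and must not be counted as failures.
3. Show patients who stopped because of remission as a separate row.
4. State how patients still on treatment but without a value in the window are handled.
5. Label the observed-case rates as conditional on remaining treated and assessed.

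Do not extend LOCF to Month 36: a Month 6 value could be carried for 30 months. Instead, clarify how the last-known-visit rule in Protocol 6.5 [3] fits with the visit windows in SAP 7.

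The cost is a few extra tables and no new data collection. The added estimate is conservative, especially for patients who stopped in remission, which is why they are shown separately.

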## **8. STATISTICAL METHODS AND ANALYSIS**

### **8.1. Statistical Methods**

#### **8.1.1. Analysis of Continuous Data**

Summary statistics (number of patients, mean, standard deviation, median, minimum, and maximum) will be calculated.

#### **8.1.2. Analysis of Categorical Data**

The frequency of each classification and the proportion will be calculated.

#### **8.1.3. Analysis of Binary Data**

Frequency and the proportion will be calculated. If a confidence interval for proportion is calculated, a 2-sided 95% confidence interval will be calculated. At the tests, unknown, unspecified, and unmeasured data will be excluded from the analysis.

If a test is performed, Fisher's exact test will be performed for a relationship with nominal scale data and Cochran-Armitage test (exact method) will be performed for a relationship with ordinal scale data.

Ratios and differences of proportions and their 95% confidence intervals will be calculated to compare proportions among treatment groups.

Risk ratios and their 95% confidence intervals will be calculated to compare proportions among subgroups.

If a model analysis is performed, a logistic regression model will be used.

#### 8.1.4. Analysis of Time-to-event

Summary statistics (median, 1st quartile, and 3rd quartile) by the Kaplan-Meier method will be calculated. In addition, a Kaplan-Meier plot will be prepared.

Time to each event and time to censoring will be separately specified for each item.

If a model analysis is performed, a Cox proportional hazard model will be used.

#### 8.1.5. Analysis of Incidence Rate and Incidence Proportion of Specified Events

Incidence rate and incidence proportion will be calculated for specified events including initial malignancy, initial serious infection, and death, according to the following formulae.

- **Duration of exposure [patient-year]**

Total of time to each event and time to censoring in each group [day]/365.25

- **Incidence rate amount and the 95% confidence interval**

$$\text{Incidence rate amount [patient/100 patient - years]} = 100 \times \frac{a}{PT}$$

95% confidence interval for incidence per exposure amount [patient/100 patient - years].

$$= \begin{cases} \left[ 100 \times \frac{x^2(0.025, 2a)/2}{PT}, 100 \times \frac{x^2(0.975, 2(a+1))/2}{PT} \right] & (a \neq 0) \\ \left[ 0.00, 100 \times \frac{x^2(0.95, 2))/2}{PT} \right] & (a = 0) \end{cases}$$

a: Number of patients with the event [patient]

PT: Duration of exposure [patient-year]

$x^2(p, d)$ : the lower p quantile for the chi - square distribution with d degrees of freedom

- **Incidence proportion and the 95% confidence interval**

$$\text{Incidence proportion [%]} = 100 \times \frac{a}{N}$$

95% confidence interval for incidence proportion [%]

$$= \left[ 100 \times \left( 1 + \frac{N - a + 1}{aF(0.025, 2a, 2(N - a + 1))} \right)^{-1} \cdot 100 \times \left( 1 + \frac{N - a}{(a + 1)F(0.975, 2(a + 1), 2(N - a))} \right)^{-1} \right]$$

N: Number of patients included in the analysis [patient]

$F(p, m, n)$ : the lower  $p$  quantile for the F distribution with  $m$  and  $n$  degrees of freedom.

### 8.1.6. Group Comparison of Incidence Rate and Incidence Proportion of Specified Events

Specified events including initial malignancy, initial severe infection, and death will be compared between groups in terms of the following quantities:

- **Incidence ratio between the treatment groups and the 95% confidence interval**

$$\text{Incidence ratio} = \frac{a/\text{PT}_1}{b/\text{PT}_0}$$

95% confidence interval for incidence ratio

$$= \exp \left[ \left\{ \ln \left( \frac{a/\text{PT}_1}{b/\text{PT}_0} \right) \pm 97.5 \text{ percentile for standard normal distribution} \times \sqrt{\frac{1}{a} + \frac{1}{b}} \right\} \right]$$

Xeljanz group a: Number of patients with the event [patient], PT1: Duration of exposure [patient-year]

Control group b: Number of patients with the event [patient], PT0: Duration of exposure [patient-year]

- **Difference in incidence rates between treatment groups and its 95% confidence interval**

Difference in incidence rates [patient/100 patient-years]

$$= 100 \times \left( \frac{a}{\text{PT}_1} - \frac{b}{\text{PT}_0} \right)$$

95% confidence interval for difference in incidence rates [patient/100 patient-years]

$$= 100 \times \left\{ \left( \frac{a}{PT_1} - \frac{b}{PT_0} \right) \pm 97.5 \text{ percentile for standard normal distribution} \right. \\ \left. \times \sqrt{\frac{a}{PT_1^2} + \frac{b}{PT_0^2}} \right\}$$

- **Ratio of incidence proportions between treatment groups and its 95% confidence interval**

$$\text{Ratio of Incidence proportions} = \frac{a/N_1}{b/N_0}$$

95% confidence interval for ratio of incidence proportions

$$= \exp \left[ \left\{ \ln \left( \frac{a/N_1}{b/N_0} \right) \pm 97.5 \text{ percentile for standard normal distribution} \right. \right. \\ \left. \left. \times \sqrt{\frac{1}{a/N_1} + \frac{1}{b/N_0}} \right\} \right]$$

Xeljanz group

$N_1$ : Number of patients included in the analysis [patient]

Control group

$N_0$ : Number of patients included in the analysis [patient]

- **Difference in incidence proportion between the treatment groups and the 95% confidence interval**

$$\text{Difference in incidence proportion [%]} = 100 \times \left( \frac{a}{N_1} - \frac{b}{N_0} \right)$$

95% confidence interval [%] for the difference in incidence proportion

$$= 100$$

$$\times \left\{ \left( \frac{a}{N_1} - \frac{b}{N_0} \right) \pm 97.5 \text{ percentile for standard normal distribution} \right. \\ \left. \times \sqrt{\frac{a(N_1 - a)}{N_1^3} + \frac{b(N_0 - b)}{N_0^3}} \right\}$$

- **Pooled incidence ratio between the treatment groups and the 95% confidence interval**

$$\text{Pooled incidence ratio} = \frac{\sum \left( \frac{a_i PT_{0i}}{T_i} \right)}{\sum \left( \frac{b_i PT_{1i}}{T_i} \right)}$$

95% confidence interval for pooled incidence

$$= \exp \left( \ln \left[ \frac{\sum \left( \frac{a_i PT_{0i}}{T_i} \right)}{\sum \left( \frac{b_i PT_{1i}}{T_i} \right)} \right] \pm 97.5 \text{ percentile for standard normal distribution} \right)$$

$$\times \sqrt{\frac{\sum \left( \frac{M_{1i} PT_{1i} PT_{0i}}{T_i^2} \right)}{\left( \sum \frac{a_i PT_{0i}}{T_i} \right) \left( \sum \frac{b_i PT_{1i}}{T_i} \right)}}$$

Xeljanz group

$a_i$ : Number of patients with the event in Stratum i [patient]

$PT_{1i}$ : Duration of exposure in Stratum i [patient-year]

Control group

$b_i$ : Number of patients with the event in Stratum i [patient]

$PT_{0i}$ : Duration of exposure in Stratum i [patient-year],

$$M_{1i} = a_i + b_i$$

$$T_i = PT_{1i} + PT_{0i}$$

- **Difference in pooled incidence rates between treatment groups and its 95% confidence interval**

